11. CORRELATIVE / SPECIAL STUDIES

11.1 Background

Hemophagocytic syndrome is driven by inflammatory cytokines, including interferon- γ , that culminate in STAT1 phosphorylation, activated T-cell accumulation, and macrophage activation.

11.2 Rationale for Analysis

We will utilize immunofluorescent staining (by flow cytometry) to test the hypothesis that ruxolitinib inhibits Stat1 activation in HPS. We will evaluate the expression of Stat1 and pStat1 in peripheral blood T-cells and monocytes pre- and post-treatment. The post-treatment analysis will be conducted 7 (+/- 3) days following treatment initiation. T-cell (sIL-2R) and macrophage (soluble CD163) activation markers will be serially analyzed by ELISA in patient plasma. Plasma samples will be obtained weekly and cryopreserved for analysis of relevant cytokines (including interferon- γ) by ELISA. We will test the hypothesis that ruxolitinib decreases inflammatory markers (e.g. soluble CD163) associated with macrophage activation.

11.3 Collection of Specimens

Research blood samples (\approx 20 mL) will be obtained prior to treatment, and every 7 days (+/-2 days) thereafter.

Handling of Specimens

All specimens are to be shipped to the [name] laboratory at the address below. Lab personnel will re-label the specimen using a code specific for this trial. Peripheral blood mononuclear cells will be isolated by density centrifugation and viably frozen using laboratory standard operating procedures. Platelet-poor plasma will be isolated using laboratory standard operating procedures and cryopreserved.

[name] laboratory
[name]
[name]
[name]

12. STUDY PARAMETERS AND CALENDAR

12.1 Study Parameters

12.1.1 Screening Evaluation

Screening studies and evaluations will be used to determine the eligibility of each subject for study inclusion. All evaluations must be completed no longer than 14 days prior to administration of protocol therapy.

- Informed Consent
- Medical History
- Complete physical examination
- Vital signs including: blood pressure, pulse, respiratory rate, weight and temperature
- Concomitant Medications Assessment including prescription and herbal supplements
- Laboratory Studies:
 - Complete Blood Count (CBC) with differential and platelets.
 - Serum Chemistries: albumin, alkaline phosphatase, total bilirubin, bicarbonate, BUN, calcium, chloride, creatinine, glucose, potassium, total protein, SGOT [AST], SGPT [ALT], sodium.
 - β -HCG for women of childbearing potential at time of study entry
 - Ferritin
 - Lipids (Triglycerides)
 - Fibrinogen
 - Soluble IL-2 receptor
 - NK cell activity

12.2 Calendar

	Enrollment (within 14 days of treatment)	Pre-treatment (within 48 hours of treatment)	Weekly (weeks 1-5) ⁴ (beginning day 7, +/- 2 days)	q14 days +/- 3 days (weeks 6-12)⁴	q28 days +/- 3 days (>12 weeks)⁴
Informed consent	X				
H&P (including medication review)	X	X	X	X	X
CBC ¹	X	X	X	X	X
Serum Chemistries (including AST/ALT)	X	X	X	X	X
Pregnancy test ⁵	X				
Ferritin	X	X	X	X	X
Lipids	X	X	X	X	
Fibrinogen	X	X	X	X	
sIL-2 Receptor	X	X	X	X	
NK cell activity ²	X	X	X		
Research blood draw ³		X	X		
Collect Adverse Events	X	X	X	X	X

¹Performed at least every 72 hours for weeks 1-5 of treatment. ²May be performed every 7-14 days. If total lymphocytes are insufficient to measure NK cell activity during enrollment, repeat testing is not required. ³Four heparin tubes (≈20 mL total volume) will be collected. Peripheral blood mononuclear cells and platelet-poor plasma will be obtained and cryopreserved for ancillary studies. Research blood draws will cease 14 days after a CR is achieved or after 5 weeks of treatment, whichever comes first. ⁴Study procedures required for response assessments and toxicity monitoring will be performed every two weeks (Bi-weekly) for patients who remain on treatment >6 weeks. For patients who remain on treatment >12 weeks, the following procedures will be performed monthly: H&P, CBC, serum chemistries, ferritin, and adverse events. ⁵Pregnancy testing will be performed every 6 weeks (+/- 7 days) in women of child-bearing potential.

13. MEASUREMENT OF EFFECT

13.1 Response evaluation

13.1.1 Definitions

Evaluable for toxicity. All patients will be evaluable for toxicity from the time of their first treatment with Ruxolitinib.

Evaluable for objective response. Only those patients who received at least 7 days of therapy, and have had their disease re-evaluated will be considered evaluable for response. These patients will have their response classified according to the definitions stated below.

13.1.2 Disease Parameters

- Fever
- Splenomegaly (by physical examination or radiographic imaging).
- Cytopenias involving ≥ 2 cell lines
- Ferritin
- Triglycerides
- Fibrinogen
- Soluble IL-2 receptor
- NK cell activity

13.1.3 Response Criteria

Evaluation of Response

Response	Evaluation of Target Lesions
Complete Response (CR)	Complete normalization of all quantifiable signs and laboratory abnormalities included in the diagnostic criteria for HPS.
Partial Response (PR)	At least a 25% improvement in two or more quantifiable signs/laboratory markers.
Progressive Disease (PD)	At least a 50% worsening in two or more quantifiable signs/laboratory markers.
Stable Disease (SD)	Neither sufficient improvement to qualify for CR/PR, nor sufficient worsening to qualify for PD.

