3.4 Expected Duration of Subject Participation

3.4.1 Duration of Therapy

In the absence of treatment delays or cessation due to adverse events, treatment may continue indefinitely or until one of the following criteria applies:

- Disease progression.
- Intercurrent illness that prevents further administration of treatment.
- The investigator considers it, for safety reasons, to be in the best interest of the patient. The investigator may recommend gradual discontinuation (i.e. ruxolitinib taper) in patients achieving a prolonged response (defined as a PR or CR ≥ 6 months in duration). The rate of a ruxolitinib taper, and decisions to dose escalate in the setting of recurrent signs/symptoms, are not specified in this protocol, and are at the discretion of the investigator.
- Unacceptable adverse events such as any toxicity or other issue that causes a delay of study drug administration by more than 4 weeks.
- General or specific changes in the patient's condition render the patient unacceptable for further treatment in the judgment of the investigator.
- Patient decision to withdraw from treatment (partial consent) or from the study (full consent).

- Death.
- Sponsor reserves the right to temporarily suspend or prematurely discontinue this study.

The date and reason for discontinuation must be documented. Every effort should be made to complete the appropriate assessments.

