4.1 Inclusion Criteria

Patients must meet all of the following inclusion criteria to be eligible for enrollment:

1. Patients, or their legally authorized representative, must voluntarily provide written IRB-approved informed consent.
2. Males and females, 18 years of age or older at the time of enrollment.
3. Patients must meet the diagnostic criteria for HPS (at least 5 of the following):
 - fever
 - splenomegaly
 - cytopenia involving ≥ 2 cell lines (Hemoglobin < 9 g/dL; platelets $< 100,000/\mu\text{L}$; absolute neutrophil count $< 1000/\mu\text{L}$)
 - hypertriglyceridemia or hypofibrinogenemia
 - tissue demonstration of hemophagocytosis
 - low or absent NK cell activity
 - serum ferritin ≥ 3000 ug/L
 - soluble IL-2 receptor (CD25) > 2400 U/mL.
4. In the investigator's opinion, the patient has the ability to participate fully in the study and comply with all its requirements.

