6.2 General Concomitant Medications and Supportive Care Guidelines

Because there is a potential for interaction of Ruxolitinib with other concomitantly administered drugs through the cytochrome P450 system, the case report form must capture the concurrent use of all other drugs, over-the-counter medications, or alternative therapies. The Principal Investigator should be alerted if the patient is taking any agent known to affect CYP3A4. In patients who concurrently take strong CYP3A4 inhibitors and a platelet count of at least 50,000 the dose of ruxolitinib should be capped at 10 mg twice daily due to the concern for increased serum concentrations of ruxolitinib's active metabolites. Strong CYP3A4 inhibitors, including grapefruit juice, should be avoided whenever possible.

Patients should receive full supportive care, including transfusions of blood and blood products, cytokines, antibiotics, anti-emetics, etc when appropriate.

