15.2 Analyses

Primary:

The primary analysis is the count of patients alive after 2 months since study entry. If 4 or more patients are alive at the 2 months assessment, the null hypothesis of a 15% survival probability at 2 months will be rejected in favor of our alternative hypothesis of a 60% survival probability. Ninety-five percent confidence intervals will be constructed based upon the exact binomial confidence interval. No loss-to-follow-up or censoring is expected prior to the study's primary endpoint assessment.

Secondary:

There are no formal response criteria for secondary HPS. Therefore, efficacy assessments (including appropriate laboratory studies) will be performed weekly (weeks 1-5), and every two weeks (weeks 6-12), and monthly (after 12 weeks), and responses determined as previously reported in a retrospective study.⁸ Briefly, a complete response is defined as

complete normalization of all quantifiable symptoms and laboratory abnormalities (described in the diagnostic criteria for HPS, above). A partial response is defined as at least a 25% improvement in two or more quantifiable symptoms/laboratory markers following the initiation of treatment. The best overall response is the best response recorded from the start of the treatment until disease progression/recurrence

Follow-up time will be calculated from the first administration of ruxolitinib, until death for OS or until disease-progression or death for PFS. Patients lost to follow-up will be censored on the date of their last known clinical assessment. Specifically for DOR, only patients having at least a PR to therapy are evaluable. Duration will be calculated from the date of the determination of partial response or better until the date of progression, death, or additional non-protocol therapy. Again, for patients lost to follow-up, duration will be censored at the time of last clinical assessment. The count and percentage of the number having an objective response (CR, CRu, or PR) will be reported along with confidence intervals. Product-limit estimates of Kaplan and Meier will be used to estimate OS, PFS, and DOR. The likelihood of loss to follow-up is expected to be extremely low.

Exploratory:

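### Response scoring: a transfused blood count can help make a PR, one visit can be both PR and PD, and three HPS markers go unscheduled after week 12

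*Combined protocol and SAP*

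**What the plan says.** Section 13.1.3 calls a patient PR when two or more quantifiable signs or laboratory markers improve by at least 25%. PD is "At least a 50% worsening in two or more quantifiable signs/laboratory markers". Stable disease (SD) is whatever qualifies as none of the others. The table does not say which category wins if PR and PD are both met.

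Section 13.1.2 lists eight disease parameters, one of which is "Cytopenias involving ≥ 2 cell lines". Section 4.1 gives hemoglobin, platelets and neutrophils (ANC) each a numeric cut-off. Neither 13.1.3 nor 15.2 says how a percentage change is applied to these counts.

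Section 6.2 states: "Patients should receive full supportive care, including transfusions of blood and blood products, cytokines". Section 13.1.3 has no rule for counts measured under such support.

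Section 12.2, footnote 4, says that after week 12 "the following procedures will be performed monthly: H&P, CBC, serum chemistries, ferritin, and adverse events". Section 15.2 says that efficacy assessments "will be performed weekly (weeks 1-5), and every two weeks (weeks 6-12), and monthly (after 12 weeks". Section 3.4.1 says "treatment may continue indefinitely or until one of the following criteria applies"; progression is one of those criteria. The same section lets the investigator recommend a taper after a PR or CR of at least 6 months. For duration of response (DOR), 15.2 says: "Duration will be calculated from the date of the determination of partial response or better until the date of progression"; death and non-protocol therapy also end it.

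**The concern.** Response rate, DOR and PFS all rest on 13.1.3. Patients with HPS are cytopenic and will often need blood products. If a platelet rise after transfusion counts as improvement, part of the response rate measures supportive care rather than ruxolitinib.

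A visit that meets both PR and PD leaves the analyst to decide whether the patient is a responder. After week 12 the plan keeps assessing efficacy but stops scheduling most of the tests that define progression. Progression in an untested marker may then be dated late or missed.

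The study is open-label with 10 patients, so each such choice would be made patient by patient, by people who know the outcome.

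**Working it through.** The plan gives no figure to reproduce here. The check sets the sections side by side and works through assumed visits; all patient values below are illustrations.

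**1. Supported count and PR.** Assumed changes from pre-treatment:
- ferritin 10,000 to 7,000: (7,000 − 10,000)/10,000 = −30%
- platelets 40,000 to 55,000 after transfusion: 15,000/40,000 = +37.5%
- hemoglobin 8.0 to 8.2: 0.2/8.0 = +2.5%
- ANC 800 to 850: 50/800 = +6.25%

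Taken literally, ferritin and platelets are two markers improved by at least 25%, so the visit is PR. If the transfused count is set aside, only ferritin qualifies and the visit is SD. It is also SD if two cell lines must improve. That reading does not close the gap, because red cells can be transfused too: a hemoglobin of 8.0 needs to reach only 8.0 × 1.25 = 10.0. If each line is its own marker, two transfused lines would make a PR with nothing else improved.

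**2. PR and PD at one visit.** Assumed changes, before week 12:
- ferritin 10,000 to 6,000: −40%
- sIL-2R 8,000 to 5,000: −37.5%
- platelets 60,000 to 28,000: −32,000/60,000 = −53.3%
- ANC 900 to 430: −470/900 = −52.2%
- triglycerides 300 to 460: 160/300 = +53.3%

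Ferritin and sIL-2R give PR. Triglycerides plus the counts give PD, whether counts are scored by any one line, by two lines or separately. It is not PD only if counts are left out altogether. If this is the first PR, DOR starts and ends on the same date: 0 days. Section 15.2 takes the best response from the start of treatment until progression, but does not say whether the progression visit itself is included.

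**3. Scheduled HPS laboratory items (13.1.2 against 12.2).**
- Weeks 1-5: cytopenias, ferritin, triglycerides, fibrinogen, sIL-2R, NK activity = 6
- Weeks 6-12: NK activity stops, 6 − 1 = 5
- After week 12: triglycerides, fibrinogen and sIL-2R stop, 5 − 3 = 2 (ferritin and the blood count)

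The chemistry panel in 12.1.1 contains no HPS criterion. Fever and spleen can still be assessed at the physical examination. A patient whose sIL-2R and triglycerides both worsen by 50% after week 12 meets PD, but no scheduled test would show it.

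The taper rule falls largely in this period. Six months is about 26 weeks. A response dated at the first weekly visit (week 1) has at most 12 − 1 = 11 weeks under the fuller schedule, leaving 26 − 11 = 15 weeks under the reduced one.

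**4. Scoring of counts.** Assumed visit after week 12, no fever, spleen unchanged:
- ferritin 4,000 to 6,400: +60%
- platelets 60,000 to 28,000: −53.3%
- hemoglobin 8.5 to 8.0: −5.9%
- ANC 900 to 800: −11.1%

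If any one line, or each line separately, can score, this is PD. If two lines are needed, or counts are left out, it is SD, and the thrombocytopenia table in section 7 points to Level −2.

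**5. Size.** With 10 evaluable patients, one reclassification is 1/10 = 10 points. Exact (Clopper-Pearson) 95% intervals: 4/10 = 40% (12.2 to 73.8%); 5/10 = 50% (18.7 to 81.3%). Section 13.1.1 requires 7 days of therapy and a re-evaluation, so the denominator may be smaller and the shift larger.

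**The case against.** The strongest case on the other side has four parts.

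- **Materiality.** Section 15.2 openly says that no formal response criteria exist. This is a small pilot, and its primary endpoint is survival. That stands, and it limits the point to secondary results.
- **The calendar is a minimum.** Section 15.2 says efficacy assessments include suitable laboratory studies, and nothing bars an sIL-2R or fibrinogen test at suspected relapse. That also stands, but permitted is not required. Whether progression is found then depends on who orders the test and when.
- **The cited report.** Section 15.2 takes its response method from a published retrospective study, which may contain a counting rule. This cannot be checked here. The summary in 15.2 gives CR and PR only, with no rule for supported counts and none for a visit that meets both PR and PD.
- **Rarity.** The same-visit example needs several large opposing changes at once. It may be uncommon, and no frequency is claimed.

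A reader might go further and infer that cytopenias are a single marker, so that counts alone can never be PD and every PD after week 12 turns on the blood count. The documents do not support this. Section 13.1.3 does not equate a marker with a line of the 13.1.2 list, and 4.1 gives each cell line its own cut-off. The lists are not a reliable guide to what is one marker: 4.1 joins triglycerides and fibrinogen in one item, while 13.1.2 separates them. Fever, spleen and unscheduled tests can also contribute to PD. Nor is it right that counts have no percentage scale; what is missing is a rule for using it.

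**Conclusion.** The point holds for secondary endpoints and is worth correcting, at low to moderate importance.

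- Crediting supported counts can only raise the response rate.
- Counting a PR at a PD visit raises the response rate and adds durations of 0 days.
- Dropping three progression markers from the schedule after week 12 may overstate PFS and DOR, and it weakens the basis for the stop and taper decisions in 3.4.1. Those decisions are partly discretionary in any case: the investigator may stop treatment for safety or a change in condition without PD, and the taper is optional.

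The 2-month survival endpoint is not scored from 13.1.3 and is unaffected.

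The size is 10 points of response rate per reclassified patient among 10 evaluable. How many patients would be reclassified cannot be estimated from the documents. The conclusion assumes that the plan is applied as printed, that the cited report adds no further rule, and that the cytokines named in 6.2 include growth factors that raise counts.

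**What to change.** 1. In 13.1.3 add: *A blood count supported by transfusion or growth factor in the preceding 7 days does not count toward PR or CR.* The 7-day window is a proposal; it matches the visit interval in weeks 1-5.
2. In 13.1.3 add: *If PR and PD criteria are both met at one visit, PD is recorded and the visit is not counted as a response.*
3. In 12.2, require sIL-2R, triglycerides and fibrinogen after week 12, at least when progression is suspected, from blood drawn at the existing visit.
4. State in 13.1.3 whether hemoglobin, platelets and ANC count as one marker or separately. Report the alternative readings, including each line as its own marker, as a sensitivity analysis.

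A rule that two lines must change should not be imposed. Take a patient with two low lines whose platelets go from 40,000 to 150,000 (110,000/40,000 = +275%) while hemoglobin goes from 8.0 to 8.5 (+6.25%) and a normal ANC stays stable. This patient no longer has two cytopenic lines, yet would be scored as not improved.

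The cost is a few sentences, a few extra blood tests and possibly a slightly lower response rate. No change to the sample size or the primary analysis is needed.

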13.1.4 Duration of Response

Duration of overall response: The duration of overall response is measured from the time measurement criteria are met for CR or PR (whichever is first recorded) until the first date that recurrent or progressive disease is objectively documented. The duration of overall CR is measured from the time criteria are first met for CR until the first date that progressive disease is objectively documented.

Duration of stable disease: Stable disease is measured from the start of the treatment until the criteria for progression are met.

14. RECORDS TO BE KEPT / REGULATORY CONSIDERATIONS

Adverse event lists, guidelines, and instructions for AE reporting can be found in Section 8.0 (Adverse Events: List and Reporting Requirements).

14.1 Data Reporting

The Velos Database will be utilized, as required by the UNIVERSITY OF MICHIGAN COMPREHENSIVE CANCER CENTER, to provide data collection for both accrual entry and trial data management. Velos is designed with the capability for study setup, activation, tracking, reporting, data monitoring and review, and eligibility verification. This study will utilize electronic Case Report Form completion in the Velos database. A calendar of events and required forms are available in Velos.

14.2 Regulatory Considerations

The study will be conducted in compliance with ICH guidelines and with all applicable federal (including 21 CFR parts 56 & 50), state or local laws.

14.2.1 Written Informed consent

Provision of written informed consent must be obtained prior to any study-related procedures. The Principal Investigator will ensure that the subject is given full and adequate oral and written information about the nature, purpose, possible risks and benefits of the study as well as the subject's financial responsibility. Subjects must also be notified that they are free to discontinue from the study at any time. The subject should be given the opportunity to ask questions and allowed time to consider the information provided.

The original, signed written Informed Consent Form must be kept with the Research Chart in conformance with the institution's standard operating procedures. A copy of the signed written Informed Consent Form must be given to the subject.

14.2.2 Subject Data Protection

In accordance with the Health Information Portability and Accountability Act (HIPAA), a subject must sign an authorization to release medical information to the manufacturer and/or allow the manufacturer, a regulatory authority, or Institutional Review Board access to subject's medical information that includes all hospital records relevant to the study, including subjects' medical history.

14.2.3 Accessing Electronic Medical Records for University of Michigan Hospital and Health Systems

This study will access electronic medical records systems to obtain medical information for the subjects enrolled to this study.

In order to insure patient safety, investigators and study personnel must have up-to-the-minute health information for subjects enrolled to this study. Therefore, electronic medical records must be utilized to obtain medical information in a timely manner.

The following electronic systems will be used: MiChart to access scheduling information; MiChart and Careweb to access lab results and physician notes; MiChart and Careweb as necessary to locate archived medical records; PACS to access radiological imaging results.

Access to these systems is required for the life of this research study.

Information obtained from electronic systems will be copied into the University of Michigan Cancer Center Clinical Trials Unit research chart and/or printed (lab results, physician notes, etc.) and stored in the research chart. Research charts are kept secure and destroyed according to UH policy.

Study data will be obtained by the PI, co-investigators, study coordinator, and/or data manager for this study via password-protected login. All study personnel involved in this research will adhere to the UH policies regarding confidentiality and Protected Health Information.

